**Figure 2 – Incidence of Clinically Significant Atrial Fibrillation in the MID Study**

Source: *Roy-Chaudhury et al. 2018*

In a similar study, Sacher *et al* used an implantable loop recorder to extend the observations of Roy-Chaudry and Tumlin and determine clinical outcomes of patients with dialysis-associated arrhythmias. The incidence of specific arrhythmias was similar with 20% patients developing *de novo* atrial fibrillation or flutter with a nearly identical number developing bradycardia. Of the patients with bradycardia, 3 progressed to asystole and sudden death. An analysis of serum electrolytes at the time of the arrhythmia demonstrated that hyperkalemia was associated with conduction disorders while hypokalemia was associated with ventricular arrhythmias and atrial fibrillation (*Sacher et al. 2018*). More recently, Ohnishi et.al conducted a cohort study of 3967 participants in the Dialysis Outcomes and Practice Patterns Study in Japan (DOPPS-Japan) and examined the long-term effects of post-dialysis hypokalemia on all-cause mortality and the incidence of cardiac mortality due to sudden death. As a part of the original observational protocol, participating patients had post-dialysis serum potassium ( $K^+$ ) measured every 4 months. Patients were then divided into quartiles based upon the average post dialysis  $K^+$ . As can be seen in **Figure 3**, patients with low post-dialysis  $K^+$  ( $< 3.0$  mEq/L) had significantly reduced survival with a hazard mortality of 1.89 (*Ohnishi et al. 2019*). These observations underscore the sensitivity of ESRD patients to electrolyte induced cardiac arrhythmia. Moreover, it points to the need to and the need to identify a “ $K^+$  safety range” and to individualize dialysate baths to achieve optimal before, after and during dialysis.

[figure not shown]

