## 2.3 Safety Objectives

Safety Objective #1: Lokelma-Induced Hypokalemia	Safety Outcome Measure:
To evaluate whether the use of oral sodium zirconium cyclosilicate (Lokelma ® ) during periods when patients are receiving a 3.0 K + /2.5 Ca ++ dialysate bath is associated with hypokalemic events defined as K + <3.5 mEq/L.	➤ Total number of hypokalemic events defined as Piccolo POCT or laboratory-measured K + of < 3.5 mEq/L.
Safety Objective #2: Incidence of Dialysis-related Hypokalemia, Hypomagnesemia, Hypophosphatemia, or Low Calcium	Safety Outcome Measure:
To determine the levels of K + , Mg ++ , calcium and PO 4 during dialysis (measured promptly prior to the termination of dialysis) during experimental treatment [2] compared to standard treatment [3]. Note: Each electrolyte is its own "safety" objective independently.	➤ Number of events (measured promptly prior to the termination of dialysis) where a Piccolo POCT measurement of K + is < 3.5 mEq/L OR Ca ++ is < 7.0 mEq/L, OR Mg ++ is < 2.0 mg/dl, OR a PO 4 level is <3.0 mEq/L. All episodes where a specific electrolyte falls below the above listed threshold will be considered an "event" for that electrolyte. The total number of "events" will be recorded during the 8-week Treatment Phase-1 and the 8-week Treatment Phase-2 cross-over periods.
Safety Objective #3: Adverse Experiences	Safety Outcome Measure:
To evaluate the safety and tolerability of the experimental treatment [2] compared to standard treatment [3] based on the frequency of reported adverse experiences.	➤ Frequencies of AEs, SAEs, and withdrawals due to AEs, with focus on treatment-related events.

Abbreviations: AE=adverse event; CSCA=clinically significant cardiac arrhythmia; SAE=serious adverse event

[2] Experimental treatment (8 weeks): hemodialysis using 3.0K+/2.5 Ca++ dialysate bath, with sodium zirconium cyclosilicate (Lokelma®) supplementation on off-treatment days

[3] Standard treatment (8 weeks): hemodialysis using 2.0K+/2.5 Ca++ dialysate bath, without sodium zirconium cyclosilicate (Lokelma®) supplementation

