### **3.9 Discontinuation of Investigational Product**

Patients may be discontinued from investigational product (IP) in the following situations:

- Patient decision. The participant is at any time free to discontinue treatment, without prejudice to further treatment;
- Incorrectly randomized participant where violation of the inclusion/exclusion criteria would put the participant at undue risk;
- Adverse event for which the investigator judges continued treatment may put the participant at undue risk;
- Pregnancy;
- Development of any of the following study-specific criteria for discontinuation:
  - Permanent atrial fibrillation, as determined by echocardiogram or cardiology assessment;

- Requiring for permanent placement of a cardiac pacemaker or AICD;
  - Refractory hyperkalemia ( $K^+ > 6.5$  mEq/L) while on 15 grams 4 days per week of Lokelma;
  - Hypokalemic event (defined as pre-dialysis  $K^+$  level of  $< 3.5$  mEq/L): Patients experiencing a minimum of two (2) hypokalemic events while taking Lokelma will have their Lokelma adjusted or discontinued at the discretion of the site PI;
  - Renal transplant.
- Severe non-compliance with the study protocol.

Note: patients wishing to remain in the study on treatment despite developing an adverse event may do so at the site PI's discretion, unless they remain hyperkalemic with  $K^+ > 6.5$  mEq/L after a long inter-dialytic interval (LIDI) for two (2) consecutive weeks.

Regardless of the reason for discontinuation, all reasons for discontinuation of study treatment must be documented in the electronic case report form (eCRF).

If the patient is discontinued from investigational product, the scheduled study visits, data collection and procedures should continue according to the study protocol until study completion, unless the patient withdraws consent for any further study procedures and follow-up. The approach taken should be documented in the eCRF.

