**Table 1 Study Plan and Schedule of Assessments**

Study Period / Visit	Screening	ILR Insertion by EP cardiologist	Baseline/ Randomization	New Dialysate Accommodation Period 1	Treatment Phase 1	Cross-over	New Dialysate Accommodation Period 2	Treatment Phase 2	ILR Removal by EP cardiologist	End of Study	Reference to Protocol Section
Study Week (Wk) [* , ** or ***]	-4 to -3**	-2*	1**	1 & 2**	3 to 10**	11**	11 & 12**	13 to 20**	21-22*	22-23***	
Study Day (D)	-28 to -15	-14	1	1 to 14	15 to 70	71	71 to 84	85 to 140	Between D141 and D155	Within 1 to 14 days after ILR Removal	
Pregnancy Test for Females of Childbearing Potential	X										

Abbreviations: AE=adverse event; Ca=calcium; ECG=electrocardiogram; EP=electrophysiologist; ILR=insertable loop recorder; K=potassium; Mg++=magnesium; PBUTs=protein-bound uremic toxins [including p-Cresol sulfate [PCS], indoxyl sulfate, and asymmetric dimethylarginine [ADMA)]; SAE=serious adverse event

\*Performed on any day. (Note: ILR placement needs to be one week prior to baseline, which starts on Mondays or Tuesdays after each long dialysis weekend.)

\*\*Performed weekly, on Mondays or Tuesdays after each long dialysis weekend. (Note: Screening ICF can be obtained on any dialysis day, but all other procedures need to be performed on Monday or Tuesdays after the long dialysis weekend. Additionally, consenting may be conducted several weeks prior to other study procedures depending on the need for a prohibited medication washout or whether the consenting process occurred on a day other than the Monday or Tuesday after the long dialysis weekend.)

\*\*\*Performed on any dialysis day

[1] K+ Piccolo POCT (utilizing full renal panel) are performed pre-dialysis, on a Monday or Tuesday after the long dialysis weekend, twice during the Screening period, and weekly during the treatment period (both 2-week accommodation periods and 8-week Treatment phases). Note: K+ Piccolo POCT may be performed several weeks after consenting depending on the need for a prohibited medication washout or whether the consenting process occurred on a day other than the Monday or Tuesday after the long dialysis weekend.

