## **5.3 Safety Protocols**

### **5.3.1 Safety Protocol for Patients with Piccolo POCT-Confirmed Hypokalemia or Hyperkalemia**

Hyperkalaemia will be defined as a  $K^+ \geq 7.0$  mEq/L and measured using Piccolo POCT technology in pre-dialysis obtained after the long dialysis “weekend”. Unless clinically unstable, patients with hyperkalaemia will be dialyzed and managed according to the judgment of the Site PI. Dose adjustments of Lokelma will be with each patient prior to discharge.

Hypokalemia is defined as pre-dialysis  $K^+$  level of  $< 3.5$  mEq/L. Patients experiencing a minimum of two (2) hypokalemic events while taking Lokelma will have their Lokelma adjusted or discontinued at the discretion of the site PI.

Patients with clinically significant cardiac arrhythmias including bradycardia, ventricular tachycardia, and asystole that are recognized by the dialysis staff during an individual dialysis session will be managed according to site unit protocols and include necessary resuscitation and transfer to the nearest emergency department.

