#### **8.4.6 Safety Endpoint #1: Lokelma Induced Hypokalemia**

To evaluate whether the use of Lokelma during periods when patients are receiving a 3.0 K+/2.5 Ca++ bath is associated with hypokalemic events, the total number of hypokalemic events (defined as Piccolo POCT or laboratory-measured K+ of < 3.5 mEq/L) will be summarized.

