#### **8.5.6 Safety Analyses**

Lokelma-induced hypokalemia will be evaluated based on the total number of hypokalemic events defined as PiccoloPOCT or laboratory-measured K+ of < 3.5 mEq/L.

The incidence of dialysis-related hypokalemia, hypomagnesemia, hypophosphatemia, and low calcium will be evaluated based on the number of events promptly prior to the termination of dialysis where a PiccoloPOCT measurement of K+ is < 2.0 mEq/L OR Ca++ is < 7.0 mEq/L, OR Mg++ is < 2.0 mg/dl, OR a PO4 level is < 3.0 mEq/L. All episodes where a specific electrolyte falls below the above listed threshold will be considered an “event” for that electrolyte. The total number of “events” will be recorded during the 8-week Treatment Phase-1 and the 8-week Treatment Phase-2 cross-over periods and compared between the treatments.

Safety will also be assessed in terms of the frequency of AEs, SAEs, and withdrawals due to AEs, with focus on treatment-related events. Appropriate summaries of these data will be presented by treatment group and/or study period.

Adverse events will be coded using the Medical Dictionary for Regulatory Activities (MedDRA) system organ class (SOC) and preferred term (PT). A treatment-emergent AE

(TEAE) is defined as an AE with the start date on or after the first dose date and up to (and including) 14 days after the last dose date in each of study periods when patients received 3K Bath with Lokelma. However, when patients received 2K Bath without Lokelma, A treatment-emergent AE (TEAE) is defined as an AE with the start date on or after the first visit date and up to (and including) 14 days after the last visit date in each of study periods. Only TEAEs will be included in table summaries.

The number and percentage of participants experiencing AEs, SAEs, AEs that led to withdrawal, AEs that led to death, and the number of such events, will be summarised by SOC, PT, and treatment group and study period. The number and percentage of participants experiencing AEs will further be summarised by intensity and will be presented with the number of events at each level of intensity.

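### Safety Endpoint #1 pools pre-dialysis and end-of-dialysis potassium below 3.5 mEq/L, so its count cannot be attributed to Lokelma and could hide a pre-dialysis excess

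*Protocol*

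**What the plan says.** The synopsis and Section 2.3 give the outcome for Safety Objective #1, Lokelma-induced hypokalemia, as "Total number of hypokalemic events defined as Piccolo POCT or laboratory-measured" K+ below 3.5 mEq/L. Section 8.4.6 says that, to evaluate whether Lokelma use on the 3.0 K+ bath "is associated with hypokalemic events, the total number of hypokalemic events" will be summarised. It repeats the event as "defined as Piccolo POCT or laboratory-measured K + of < 3.5 mEq/L", and 8.5.6 states that "Lokelma-induced hypokalemia will be evaluated based on the total number of hypokalemic events" on the same definition. None of these places gives a sampling time.

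Two K+ measurements are scheduled each week. Table 1, note 1, sets the pre-dialysis one, "twice during the Screening period, and weekly during the treatment period". Note 2 sets a second one just before dialysis ends, within 30 minutes before rinse back.

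Elsewhere the event is narrower. Section 3.9 has "Hypokalemic event (defined as pre-dialysis" K+ below 3.5, Section 5.3.1 has "Hypokalemia is defined as pre-dialysis" K+ below 3.5, and Section 6.9 uses the same pre-dialysis definition for its IP-related events.

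End-of-dialysis K+ already has its own endpoint, Safety Endpoint #2, whose title calls it dialysis-related. Section 5.2.1 says that the counts will be compared between the two treatments.

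**The concern.** The endpoint is named for what Lokelma causes, but as worded it accepts any low K+ whenever it was drawn. An end-of-dialysis value reflects the potassium that the session has just removed as well as the level at which the patient arrived. A pre-dialysis value after the long interval is closer to what an off-dialysis-day binder would change.

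The trial changes bath and binder together, and at the end of dialysis they are expected to act in opposite directions: the higher bath should leave K+ higher, the binder lower. If end-of-dialysis lows make up most of the total, the comparison mainly describes the bath. A rise in pre-dialysis lows during Lokelma treatment could then sit inside a pooled count that favours the experimental treatment. Choosing the sampling time after the data are seen would be open to question.

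**Working it through.** The protocol states no event rate or power for this endpoint, so there is no figure to reproduce. The check compares the definitions, counts the samples and gives one illustration.

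**1. The definitions side by side**

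| Place | Event | Sampling time |
|---|---|---|
| Synopsis, 2.3, 8.4.6, 8.5.6 (Safety Endpoint #1) | K+ < 3.5 | none stated |
| 3.9, 5.3.1, 6.9 | K+ < 3.5 | pre-dialysis |
| Synopsis, 2.3 (Safety Endpoint #2) | K+ < 3.5 | end of dialysis |
| 8.4.7, 8.5.6 (Safety Endpoint #2) | K+ < 2.0 | end of dialysis |

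Under the objectives' threshold of 3.5, every low end-of-dialysis K+ falls under both safety endpoints. Under the 2.0 of 8.4.7 and 8.5.6, only values below 2.0 do.

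**2. Scheduled values (Table 1, notes 1 and 2)**

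- Per patient in an 8-week phase: 8 × 2 = 16, of which 8 (50%) are end-of-dialysis.
- All 88 randomized patients: 88 × 16 = 1,408 in the experimental phase. With 80 completers: 80 × 16 = 1,280.
- Counting the two accommodation weeks as well gives 10 × 2 = 20 per patient, still half end-of-dialysis.

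**3. Which lows to expect**

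Screening requires pre-dialysis K+ of 5.1 to 6.5 (3.1), and Lokelma is titrated to keep K+ between 4.0 and 5.5 (7.2.1), so pre-dialysis values below 3.5 should be uncommon. Section 1.2 says that K+ during dialysis can fall to 2.0 or lower, and offers the 3.0 bath as the way to reduce hypokalemia-induced arrhythmias. On that premise, end-of-dialysis lows should be more frequent on the 2.0 bath.

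**4. Illustration (means and SDs are assumptions, not protocol figures)**

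K+ is taken as normal, and P(K+ < 3.5) = Φ((3.5 − mean)/SD). Pre-dialysis: SD 0.6, mean 5.5 on standard treatment and 4.6 to 5.2 on experimental. End of dialysis: SD 0.45, mean 3.6 to 4.2 on the 3.0 bath and 0.3 to 0.5 lower on the 2.0 bath.

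One case, with experimental means of 5.0 (pre) and 3.9 (end) and a bath difference of 0.3:

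- Experimental pre: Φ((3.5 − 5.0)/0.6) = Φ(−2.50) = 0.0062
- Experimental end: Φ((3.5 − 3.9)/0.45) = Φ(−0.89) = 0.187
- Standard pre: Φ((3.5 − 5.5)/0.6) = Φ(−3.33) = 0.00043
- Standard end: Φ((3.5 − 3.6)/0.45) = Φ(−0.22) = 0.412
- Events per patient: experimental 8 × (0.0062 + 0.187) = 1.55; standard 8 × (0.00043 + 0.412) = 3.30
- End-of-dialysis share, experimental: 0.187/(0.187 + 0.0062) = 97%
- Ratio experimental/standard: pre-dialysis only 14.5; pooled 1.55/3.30 = 0.47

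Over all 18 combinations of the assumed means and bath differences, the end-of-dialysis share runs from 64% to 99%, the pre-dialysis ratio from 5.4 to 78, and the pooled ratio from 0.19 to 0.66. The pre-dialysis excess is built into the assumed means. The exercise shows that pooling can reverse such an excess, not that one exists. The pre-dialysis counts are also small: 8 × 0.0023 = 0.02 to 8 × 0.0334 = 0.27 per patient on experimental treatment.

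**The case against.** The best defence is that a safety count should be broad. Low K+ is a stated risk whatever the hour of the sample (1.3), the narrower definition in 3.9 and 5.3.1 serves to trigger action on Lokelma, and a management trigger may differ from a reporting endpoint. Samples are identified by time, so a pre-dialysis count can always be extracted. This supports keeping every low value in the report. It does not support a single pooled total under a title that attributes it to Lokelma.

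Several stronger readings are tempting, and the documents do not support them:

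- *There is no comparator.* Section 8.4.6 speaks only of summarising, and the comparison in 8.5.6 is attached to Safety Endpoint #2. But 5.2.1 promises a between-treatment comparison of K+ < 3.5 events, and 8.5.6 leaves full safety detail to the SAP.
- *End-of-dialysis lows are unrelated to the drug.* Lokelma is titrated to lower pre-dialysis K+, the level from which each session starts, so end values can fall too. They cannot be attributed to Lokelma, which is a weaker statement.
- *About half of post-dialysis values lie below 3.5.* A reader might infer this from the Japanese cohort in 1.1.1, where "Patients were then divided into quartiles based upon the average post dialysis" K+. Figure 3 shows fixed cut-points (3.0, 3.5, 4.0), no group sizes are given, the grouping described is on averages rather than single samples, and the bath is not stated.
- *Every low end value is counted twice.* That holds only under the objectives' 3.5 threshold, and the two endpoints are reported separately, never summed.

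**Conclusion.** The point holds in this form: the wording of Safety Endpoint #1 mixes two kinds of low K+, conflicts with the pre-dialysis definition in 3.9, 5.3.1 and 6.9, and yields a total that cannot be attributed to Lokelma. The firm figure is that 8 of 16 scheduled values per patient per phase are end-of-dialysis. How far they would dominate the count, and whether they would reverse the comparison, depends on K+ distributions that the protocol does not give; the illustrated ranges rest wholly on assumptions.

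No data are lost, and the primary endpoint is untouched. Nor would a pre-dialysis count isolate Lokelma strictly, since bath and binder always change together. But the higher bath would tend to raise K+, so an excess of pre-dialysis lows on experimental treatment would still point to the binder. The pooled count does not allow that reading.

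**What to change.** For the analysis endpoint only:

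- In the synopsis, 2.3, 8.4.6 and 8.5.6, make the count of pre-dialysis K+ < 3.5 mEq/L the measure for Safety Endpoint #1. Section 5.2.1 repeats the untimed definition and should be aligned.
- Report end-of-dialysis K+ < 3.5, and any other laboratory K+ < 3.5, as separate counts, so that no low value drops out. Simply moving end-of-dialysis K+ to Safety Endpoint #2 would, under the < 2.0 of 8.4.7 and 8.5.6, leave values from 2.0 to below 3.5 in neither endpoint.
- Present each count for both treatments with the comparison that 5.2.1 promises, and state that the contrast is bath plus binder.
- Reconcile the Safety Endpoint #2 potassium threshold between the objectives (3.5) and 8.4.7 and 8.5.6 (2.0).

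The cost is wording and matching table shells. Both samples are already scheduled, so no new data are needed. No dose or stopping rule is proposed.

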#### **8.4.7 Safety Endpoint #2: Incidence of Dialysis-related Hypokalemia, Hypomagnesemia, Hypophosphatemia, or Low Calcium**

This endpoint is defined as the number of events promptly prior to the termination of dialysis where a Piccolo POCT measurement of  $K^+$  is  $< 2.0$  mEq/L OR  $Ca^{++}$  is  $< 7.0$  mEq/L, OR  $Mg^{++}$  is  $< 2.0$  mg/dl OR a  $PO_4$  level is  $< 3.0$  mEq/L.

All episodes where a specific electrolyte falls below the above listed threshold will be considered an “event” for that electrolyte. The total number of “events” will be recorded during the 8-week Treatment Phase-1 and the 8-week Treatment Phase-2 cross-over periods. Each electrolyte will be its own “safety” objective independently.

#### **8.4.8 Safety Endpoint #3: Adverse Experiences**

The frequencies of AEs, SAEs, and withdrawals due to AEs will be summarized, with focus on treatment-related events.

### **8.5 Methods for statistical analyses**

This section is a summary of the planned statistical analyses of the most important endpoints including primary and secondary endpoints.

#### **8.5.1 General Considerations**

Inference concerning the primary analysis will be performed at the 2-sided 5% significance level. All point estimates will be presented together with confidence intervals of 2-sided 95% coverage.

The analysis assumes that there is no carry-over effect given that the wash-out period is deemed appropriate to rule out this effect by design.

Intercurrent events are handled as outlined within each section for the primary and secondary endpoint analyses below. For the primary endpoint and secondary endpoints, missing data will occur in the case where participants are lost to follow-up, provide insufficient evaluable data, withdraw consent, or die during the study. The proportion of participant missing data will be presented as appropriate.

For each participant, baseline is defined as the last available assessment prior to or on the date of the randomization visit, unless otherwise specified. A period baseline is defined as the last available assessment prior to or on the date of each of periods

In general terms, the Full Analysis Set (FAS) will be used for the efficacy analyses and the Safety Analysis Set will be used for the safety analyses.

In general, all baseline characteristics and efficacy and safety variables will be summarized using descriptive statistics as appropriate. Continuous variables will be summarized by descriptive statistics including number of participants (n), mean, standard deviation, minimum, median, and maximum. Categorical variables will be summarized using frequencies and percentages, where the denominator of the calculation is the underlying analysis set population unless otherwise stated.

Descriptive statistics of quantitative efficacy and safety parameters by scheduled visits will be provided on observed cases (i.e., including only participants who have non-missing assessments at a given visit).

### **8.5.1.1 COVID Considerations**

It is anticipated that additional sensitivity and supplementary analyses will be required to determine the impact of the COVID-19 pandemic on this trial and its endpoints. Planned sensitivity analyses will distinguish between pandemic and non-pandemic-related intercurrent events in terms of the approach taken for sensitivity analyses. Further details will be included in the SAP.

### **8.5.2 Analysis of the Primary Variable**

The primary efficacy endpoint is the frequency of atrial fibrillation events occurring during the 8-week Treatment Phase-1 and the 8-week Treatment Phase-2 dialysate cross-over periods.

The primary analysis will test the null hypothesis that there is no difference in the rate of atrial fibrillation events between the 3.0K+ dialysate bath with Lokelma and the 2.0K+ dialysate bath without Lokelma, against the alternative hypothesis that there is a difference in the rate of atrial fibrillation events between the 3.0K+ dialysate bath with Lokelma and the 2.0K+ dialysate bath without Lokelma. Statistical hypothesis testing will be completed at a 2-sided 0.05 significance level.

The primary analysis will not account for missing values. However, sensitivity analyses will be conducted using the pattern mixture model with multiple imputation (PM-MI) method. Details of the PM-MI method will be provided in the SAP.

A generalized linear model assuming the distribution of negative binomial will be used, with fixed effect terms for the treatment groups (3.0K+ dialysate bath with Lokelma and 2.0K+ dialysate bath without Lokelma), the study period, and log (the duration of period) as an offset variable. An unstructured working variance-covariance will be employed. Additional model terms may be included, details of which will be described in the SAP. The estimated risk ratio between groups and its 95% robust confidence interval (CI) will be displayed. The null hypothesis will be rejected if the p-value (based upon the Wald statistics) is less than 0.05.

